6.3 Population Rationale

As this is a Phase I study assessing the mass balance, PK and safety of MD1003, the most relevant population is healthy volunteers. Subjects who are non-smokers without a history of alcohol or drug abuse are proposed to avoid interaction on drug metabolism and to avoid non-compliance.

We acknowledge the ARSAC Notes for Guidance recommend that wherever possible, healthy subjects selected for research projects should be aged over 50 years [11]. However, the current study is designed to generate data for supporting the investigation of the human ADME of a drug, as well as generating samples for metabolite profiling and structural identification.

There are 2 main reasons for generating these data within a clinical development programme. The first is to provide human metabolite data that can be used to interpret the metabolism profiles seen in the preclinical species employed in the longer term toxicity studies, to ensure that there is adequate toxicology coverage for the safe development of the drug in patients. The second is to provide data to understand how the drug is processed in physiologically normal subjects, because understanding the routes of metabolism and elimination in a healthy population generates the appropriate data to guide the clinical pharmacology package required to fulfil the regulatory requirements of a New Drug Application.

In order to address these 2 main aims of an ADME study, investigation of the drug under development is required in a population with normal physiological function, as it is recognised that certain physiological processes eg renal function, deteriorate with age and therefore it is preferable to use as healthy as possible population, to mitigate against factors which may make interpretation of the data difficult. Also, healthy subjects as a trial population are ideal since they have a relatively stable physiological, biochemical and hormonal status, which removes any disease-related variations and variations due to concomitant medications. Therefore given the aims of this ADME study our target age range for this study will be 30 to 65 years.

Based on the above considerations, including the risk of teratogenicity (see [Section 5.3.1](#)) in rabbits that cannot be excluded in humans and risks associated with radiation exposure, and to ensure homogeneity of the population, healthy male subjects, aged 30 to 65 years are considered suitable for this study.

6.4 Risks and Benefits

Adverse drug reactions from the MS-SPI and MS-ON studies in MS patients reported in the Investigator's Brochure [1] are listed in [Table 2](#). There are no expected serious adverse reactions for either healthy volunteers or patients administered MD1003. It is unlikely that healthy volunteers administered a single 100 mg dose of MD1003 will experience an adverse reaction. Adverse events will be treated symptomatically, if required.

The dosage form will contain a radionuclide (NMT 2.22 MBq [60.0 µCi] ¹⁴C), so subjects will be exposed to ionising radiation. The effective dose that each subject will receive from one administration will not exceed 1 mSv. This is approximately 4.5 months of the average radiation exposure received in the UK each year (2.7 mSv; data obtained from PHE Ionising Radiation Exposure of the UK Population: 2010 Review). This equates to slightly more than the radiation dose that would result from 2 X-rays of the abdomen. It is believed that any increase in the amount of radiation that is received above natural radiation carries a risk of later developing serious and possibly fatal conditions. The risk associated with the maximum possible dose of radiation in this study is very small indeed and is considered to be acceptable.

Collecting a blood sample from a vein may cause pain, swelling, bruising, light-headedness, fainting, and very rarely, clot formation, nerve damage and/or infection at the site of the needle stick.

During cannulation, more than one attempt may be needed to insert the cannula in a vein of a subject and it is possible that bruising and/or inflammation may be experienced at the site of cannulation.

Electrocardiogram stickers on the subjects' chests and limbs may cause some local irritation and may be uncomfortable to remove but subjects will be closely monitored to ensure any local irritation does not persist.

There is no benefit to the subjects from taking part in this study. The development of a product to treat MS will be of benefit to the wider community/patients with this disease.

The overall risk benefit balance is therefore considered to be acceptable.

7 Objectives and Endpoints

| Objectives | Endpoints |
|--|--|
| 
Primary
 
 To determine the mass balance recovery after a single oral dose of [¹⁴C]-MD1003 To perform metabolite profiling and structural identification of MD1003 metabolites from plasma, urine and faecal samples | 
 Mass balance recovery of total radioactivity in all excreta (urine and faeces): Ae, %Ae, Cum Ae and Cum %Ae Metabolite profiling, structural identification, and quantification of [¹⁴C]-MD1003 metabolites in plasma, urine and faeces |
| 
Secondary
 
 To determine the routes and rates of elimination of [¹⁴C]-MD1003 To identify the chemical structure of each metabolite accounting for more than 10% of circulating total radioactivity To further explore the oral PK of MD1003 and its metabolites bisnorbiotin and biotin sulfoxide To evaluate the extent of distribution of total radioactivity into blood cells To provide additional safety and tolerability information for MD1003 | 
 Amount of total radioactivity excreted and amount of total radioactivity excreted as a percentage of the administered dose in urine and faeces at each time interval Identification of the chemical structure of each metabolite accounting for more than 10% by AUC of circulating total radioactivity Assessment of the oral PK profile for MD1003, bisnorbiotin, biotin sulfoxide and total radioactivity based on: Tlag, Tmax, Cmax, AUC(0-last), AUC(0-inf), AUCextrap, T1/2, Lambda-z, CL/F (MD1003 only), Vz/F (MD1003 only), MPR Cmax and MPR AUC(0-inf) Evaluation of whole blood:plasma concentration ratios for total radioactivity To provide additional safety and tolerability information for MD1003 by assessing: AEs, vital signs, electrocardiograms (ECGs), physical examinations and laboratory safety |

8 Study Design

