10.3 Study Day Procedures

10.3.1 Blood Volume

The total blood volume for each subject will not exceed 550 mL in a 4 week period.

The first 0.5 mL of blood withdrawn via cannula will be discarded.

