14.5.1 Haematology and Clinical Chemistry

Laboratory tests will be performed by The Doctors Laboratory according to the time schedule presented in [Appendix 2](#). Blood samples will be collected and processed as detailed in the Clinical Sample Processing Manual. Scheduled blood samples will be taken following an 8 h fast.

The acceptable deviations from the nominal blood sampling time points for laboratory assessments are:

- The pre-dose blood sample will be taken ≤ 2 h before dosing
- Post-dose blood samples will be taken ± 1 h from the nominal blood sampling time

Creatinine clearance (CLcr) will be calculated at screening by The Doctors Laboratory using the Cockcroft-Gault equation and body weight for eligibility purposes:

$$\text{CLcr (mL/min)} = \frac{(140 - \text{age [years]}) \times (\text{body weight [kg]}) \times 1.23}{\text{serum creatinine } (\mu\text{mol/L})}$$

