15.3 Mass Balance Data Analysis

Urine and faeces will be collected for the analysis of total radioactivity. Graphical and tabular representation of whole blood and plasma total radioactivity concentrations and ratios at selected time points will be presented. The following mass balance parameters will be calculated by Quotient Sciences for urine, faeces and combined urine and faeces (ie total radioactivity from all excreta).

| Parameter | Definition |
|------------------|---|
| Ae(urine) | Amount of total radioactivity excreted in urine |
| %Ae(urine) | Amount of total radioactivity excreted in urine expressed as a percentage of the radioactive dose administered |
| CumAe(urine) | Cumulative amount of total radioactivity excreted in urine |
| Cum%Ae(urine) | Cumulative amount of total radioactivity excreted in urine expressed as a percentage of the radioactive dose administered |
| Ae(faeces) | Amount of total radioactivity eliminated in faeces |
| %Ae(faeces) | Amount of total radioactivity eliminated in faeces expressed as a percentage of the radioactive dose administered |
| CumAe(faeces) | Cumulative amount of total radioactivity eliminated in faeces |
| Cum%Ae(faeces) | Cumulative amount of total radioactivity eliminated in faeces expressed as a percentage of the radioactive dose administered |
| Ae(total) | Amount of total radioactivity excreted in urine and faeces combined |
| %Ae(total) | Amount of total radioactivity excreted in urine and faeces combined expressed as a percentage of the radioactive dose administered |
| CumAe(total) | Cumulative amount of total radioactivity excreted in urine and faeces combined |
| Cum%Ae(total) | Cumulative amount of total radioactivity excreted in urine and faeces combined expressed as a percentage of the radioactive dose administered |

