15.6 Statistical Data Analysis

Production of summary tables, figures and listings for this study will be performed by Quotient Sciences using the statistical package SAS (v9.4 or more recent version).

No formal statistical analysis will be performed for this study. Descriptive statistics (eg mean, median, standard deviation, minimum, maximum and number of subjects with an observation [n]) are considered adequate for a study of this type. Additional statistics will be provided for PK-related data, including coefficient of variation (CV%), geometric mean, geometric CV% and geometric n (ie number of subjects with an observation that are included in the natural logarithmic transformation).

Populations and analysis sets will be determined for safety, mass balance and PK data after database lock using the criteria defined in the RAP; the RAP will be signed off prior to database lock.

Further details relating to the statistical analysis will be included in the RAP including the following:

- Criteria to be used to define each of the populations and analysis sets
- Additional detail covering the analyses and/or description of primary and secondary analyses and safety data
- Handling of missing data, unused or spurious data
- Handling of data from withdrawn subjects

All safety, mass balance recovery and PK data will be listed.

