Appendix 1 Clinical Laboratory Parameters

| Haematology | Clinical Chemistry | Virology | Urinalysis | Drugs of Abuse |
|--|--|-----------------------------|--|-----------------------------|
| Basophils | Alanine Aminotransferase (ALT) | Hepatitis B Surface Antigen | Bilirubin | Amphetamines |
| Eosinophils | Albumin | Hepatitis C Antibody | Blood | Barbiturates |
| Haematocrit (Packed Cell Volume- PCV) | Alkaline Phosphatase | HIV Antibody | Glucose | Benzodiazepines |
| Haemoglobin | Aspartate Aminotransferase (AST) | | Ketones | Cocaine |
| Lymphocytes | Bicarbonate | | Leukocytes | Marijuana/Cannabis |
| Mean Cell Haemoglobin (MCH) | Bilirubin (Total) | | Nitrites | Methadone |
| Mean Cell Haemoglobin Concentration (MCHC) | Bilirubin (Direct) (only if Total is elevated) | | pH | Methamphetamine/ Ecstasy |
| Mean Cell Volume (MCV) | Calcium | | Protein | Morphine/Opiates |
| Monocytes | Chloride | | Specific gravity | Phencyclidine |
| Neutrophils | Creatine Kinase (CK) | | Urobilinogen | Tricyclic |
| Platelet Count | Creatinine ^a | | At discretion of investigator based on urinalysis results | Antidepressants |
| Red Blood Cell (RBC) Count | Gamma Glutamyl Transferase (GGT) | | Microbiology | |
| White Blood Cell (WBC) Count | Glucose | | Urine Microscopy | |
| | Glucose (Fasting) | | | |
| | Potassium | | | |
| | Phosphate (Inorganic) | | | |
| | Protein (Total) | | | |
| | Sodium | | | |
| | Urea | | | |

^a Creatinine clearance will be calculated at screening using the Cockcroft-Gault equation for eligibility purposes

^a Discharge from clinical unit; subjects may be discharged earlier if a cumulative mass balance recovery of 90% % has been achieved or if <1% of the dose administered has been collected in urine and faeces within 2 separate consecutive 24 h periods. If the criteria are not met by Day 8, this may result in the extension of the residency period for the subjects not achieving the release criteria up to a maximum of an additional 48 h (up to Day 10) for further collection of urine and/or faeces. If the criteria are still not met by Day 10, or if additional residency is not considered appropriate or necessary, then home collections of urine and/or faeces may be requested at the discretion of the investigator for individual subjects

^b Targeted (symptom driven) physical examination

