^c Haematology and clinical chemistry at each time point including virology at screening (see [Appendix 1](#) for a full list of clinical laboratory parameters). Creatinine clearance will be estimated at screening from plasma creatinine using the Cockcroft-Gault equation for eligibility purposes

^d Blood pressure and heart rate. Oral temperature will be measured at screening, pre-dose and any unscheduled assessments as required

^e A single urine sample will be collected at pre-dose (the first void of the day) and then at the following collection periods: 0 to 12 h, 12 to 24 h, and then daily (24 h intervals) until discharge

^f Faeces will be collected pre-dose (sample to be taken between admission and pre-dose) and then daily (24 h intervals) until discharge

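### Does the blood-cell distribution objective need a blood cell:plasma ratio beside the whole blood:plasma ratio?

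*Protocol*

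**What the plan says.** Section 7, repeated in the Synopsis, sets as a secondary objective "To evaluate the extent of distribution of total radioactivity into blood cells". The endpoint against it is "Evaluation of whole blood:plasma concentration ratios for total radioactivity".

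Section 15.3 gives the planned output: "Graphical and tabular representation of whole blood and plasma total radioactivity concentrations and ratios at selected time points will be presented". Section 13.1.1 sends plasma and whole blood for radioactivity counting. Cells are not assayed separately.

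Haematocrit is in the haematology panel of Appendix 1. Footnote c of the flow chart schedules "Haematology and clinical chemistry at each time point including virology at screening", and Section 15.6 adds that "All safety, mass balance recovery and PK data will be listed". The protocol does not connect haematocrit to the blood-cell endpoint.

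All analysis is descriptive, with 6 subjects enrolled and at least 4 evaluable (Sections 15.1 and 15.6). Sections 15.4 and 15.6 leave further detail of the PK, primary and secondary analyses to the RAP, which is not among the documents reviewed.

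**The concern.** The objective asks about cells, while the endpoint is a property of whole blood. Whole blood is a mixture of cells and plasma in proportions set by haematocrit, so the ratio reflects both how much radioactivity the cells take up and how many cells there are. For the same uptake, R differs between subjects with different haematocrit unless cells and plasma hold equal concentrations.

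With 4 to 6 subjects this need not average out, and part of the between-subject spread in R could be misread as variable uptake. The question also matters for this compound: Section 5.3.4 describes possible retention over many days through trapping of biotin inside cells. Since haematocrit is measured anyway, a blood cell:plasma ratio looks like an obvious omission.

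**Working it through.** **Inputs.** The protocol states no figure for R, K or haematocrit, so there is nothing to reproduce. Assumed values: H from 0.42 to 0.48, with a wider 0.40 to 0.50 as sensitivity, and a 5% error in R for scale.

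**Formulas.** By mass balance in blood:

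- R = (1 − H) + H × K, hence R − 1 = H × (K − 1)
- K = 1 + (R − 1)/H
- gap in R between two subjects with the same K = |K − 1| × difference in H

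**What R conveys without haematocrit.** H is positive, so R − 1 and K − 1 always have the same sign: R below 1 means cells hold less than plasma, and R above 1 means they hold more, at any haematocrit. Within a subject of constant H, a change in R equals H times the change in K, so the time course keeps its shape. For a given R, moving H from 0.42 to 0.48 changes the inferred K − 1 by a factor of 0.48/0.42 = 1.14. On the wider range the factor is 0.50/0.40 = 1.25.

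**Size on the R scale, same K, two haematocrits.**

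| K | R at H = 0.42 | R at H = 0.48 | Gap | 5% of the mean R |
|---|---|---|---|---|
| 0 | 0.58 | 0.52 | 0.06 | 0.028 |
| 0.5 | 0.79 | 0.76 | 0.03 | 0.039 |
| 1 | 1.00 | 1.00 | 0 | 0.050 |
| 2 | 1.42 | 1.48 | 0.06 | 0.073 |
| 3 | 1.84 | 1.96 | 0.12 | 0.095 |

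Over the middle of the range the haematocrit gap is below the assumed error. At K = 0 and K = 3 it is above. On the wider range, K = 0.5 gives 0.80 v 0.75, a gap of 0.05, slightly above 0.039.

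**Size on the K scale, same R, two haematocrits.** Error in R is divided by H = 0.45.

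| R | K at H = 0.42 | K at H = 0.48 | Gap | 5% error in R, as K |
|---|---|---|---|---|
| 0.60 | 0.05 | 0.17 | 0.12 | 0.03/0.45 = 0.067 |
| 0.80 | 0.52 | 0.58 | 0.06 | 0.04/0.45 = 0.089 |
| 1.00 | 1 | 1 | 0 | 0.05/0.45 = 0.111 |
| 2.00 | 3.38 | 3.08 | 0.30 | 0.10/0.45 = 0.222 |

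The factor 1/H enlarges signal and error alike, so it is no argument against K by itself. But K leaves the measurement error in place and removes only the haematocrit part, which is the smaller of the two at R = 0.80.

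**What K would need.** K at each time point requires a haematocrit close in time to each radioactivity sample. Section 14.5.1 says "The pre-dose blood sample will be taken ≤ 2 h before dosing" and gives a window for post-dose samples, but the nominal times stand in a flow chart that survives here only as footnotes. Section 10.3.1 says "The total blood volume for each subject will not exceed 550 mL in a 4 week period", so drift during the stay is possible. A haematocrit off by 0.02 at H = 0.45 shifts K by about 0.04 at R = 0.60, 0.02 at R = 0.80 and 0.10 at R = 2.

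**The case for a change.** The best argument for the concern is that the pairing of objective and endpoint is fixed in the protocol itself and is not a detail passed to the RAP. The objective is about K, and R equals K only when both are 1. At the low end the difference changes the reading: R = 0.60 means K = 0 at H = 0.40, which is no entry into cells, but K = 0.20 at H = 0.50. If trapping in cells outlasts the fall in plasma, R could rise well above 1, where the gap grows again. K costs no extra sample.

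The algebra and these figures stand. They show that K would add something to the report. They do not show that R is the wrong endpoint. R comes directly from the two matrices assayed, rises strictly with K at a given haematocrit, and answers a descriptive question about extent. If late retention in cells is the interesting possibility, it would appear as a within-subject rise in R, which a stable haematocrit does not distort and which Section 15.3 already plans to show.

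The 0.40 to 0.50 contrast is also an assumption. The population is healthy men chosen for homogeneity (Section 6.3), without clinically significant abnormal haematology and without blood loss above 400 mL in the previous 3 months (Section 9.3, criteria 12 and 19), which favours a narrower spread. Whether to tabulate K, which haematocrit value to use and how to treat a negative result are the kind of detail that Sections 15.4 and 15.6 leave to the RAP, which may already settle them.

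**Conclusion.** The concern does not hold. Followed as written, the protocol gives a sound descriptive answer to its blood-cell objective: the direction of distribution does not depend on haematocrit, and the time course is kept within each subject while haematocrit is stable. The between-subject effect of haematocrit is real but modest, 0.03 in R at K = 0.5 for haematocrits of 0.42 and 0.48, rising to 0.06 at K = 0 and 0.12 at K = 3.

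These sizes rest on assumed haematocrit values and an assumed 5% error, but the conclusion does not. R is a valid measure of what the objective asks, no protocol decision depends on it, and the data needed to derive K are collected and listed, subject to how closely haematocrit and radioactivity samples coincide. Nothing is stated wrongly, contradicted or badly fixed. Reporting K as well is an optional choice for the RAP.

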8.1 Study Plan

[figure not shown]
This is a single-centre, open-label, non-randomised, single oral dose study in healthy male subjects. It is planned to enrol 6 subjects to ensure 4 evaluable subjects.

Each subject will receive a single oral administration of a capsule containing 100 mg MD1003 and NMT 2.22 MBq (approximately 60.0 µCi) [¹⁴C], in the fasted state.

The study design is presented in [Figure 1](#). Subjects will be screened to participate in the study up to 28 days before dosing. Subjects will be admitted to the clinical unit on the evening of Day -1 prior to IMP administration.

Subjects will be dosed on the morning of Day 1 following an overnight fast and will remain resident in the clinical unit until up to 168 h after dosing (up to Day 8). It is planned that subjects will be released as a group when all subjects have achieved a mass balance cumulative recovery of >90% or if <1% of the dose administered has been collected in urine and faeces within 2 separate consecutive 24 h periods. This may result in the subjects being discharged as a group prior to completion of the planned residency period. Once the discharge criteria or the planned residency period has been achieved, collection of all samples (blood, urine and faeces) will be stopped and the subjects will undergo discharge assessments. If the mass balance criteria have not been met by all subjects by Day 8, the residency period for the subjects not achieving the release criteria may be extended up to a maximum of an additional 48 h (up to Day 10) for further collection of urine and/or faeces. If the release criteria have still not been met by Day 10, or if any additional residency is not considered appropriate or necessary, then home collections of urine and/or faeces may be requested at the discretion of the investigator for individual subjects.

Figure 1 Study Sequence

^a Subject may be discharged as a group earlier if a cumulative recovery of >90% has been achieved or if <1% of the dose administered has been collected in urine and faeces within 2 separate consecutive 24 h periods. If the criteria are not met by Day 8, this may result in the extension of the residency period for the subjects not achieving the release criteria up to a maximum of an additional 48 h (up to Day 10) for further collection of urine and/or faeces. If the criteria are still not met by Day 10, or if additional residency is not considered appropriate or necessary, then home collections of urine and/or faeces may be requested at the discretion of the investigator for individual subjects.

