8.4 Subject Replacement

No replacement subjects are to be used in this study.

A subject will be considered evaluable if they have provided mass balance and PK samples for up to 72 h (up to Day 4) after IMP administration, or have demonstrated >90% mass balance recovery, or have <1% of the administered dose eliminated in excreta for 2 consecutive days, whichever is sooner.

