10.3.3 Discharge from the Clinical Unit

A subject will be allowed to leave the premises without additional investigator or delegate review, following completion of study-specific procedures at discharge, providing that:

- no AEs have been reported during the study visit
- the subject responds in the affirmative when asked if they are feeling well

Subjects will be dosed on the morning of Day 1 following an overnight fast and will remain resident in the clinical unit until up to 168 h after dosing (Day 8). It is planned that subjects will be released as a group when all subjects have achieved a mass balance cumulative recovery of >90% or if <1% of the dose administered has been collected in urine and faeces within 2 separate, consecutive 24 h periods. This may result in the subjects being discharged as a group prior to completion of the planned residency period. Once the discharge criteria or the planned residency period has been achieved, subjects will undergo discharge assessments and collection of all samples (blood, urine and faeces) will be stopped. If mass balance criteria have not been met by all subjects on Day 8, the residency period for the subjects not achieving the release criteria may be extended up to a maximum of 48 h post-dose (Day 10) for further collection of urine and/or faeces. If the criterion is still not met by Day 10, or if additional residency is not considered appropriate or necessary, then home collections of urine and/or faeces may be requested at the discretion of the investigator for individual subjects.

If any of these conditions are not met, then the subject will only be allowed to leave the clinical unit with the authorisation of the investigator or appropriately qualified delegate.

There will be no continued provision of the study intervention or treatment for subjects as this study involves healthy volunteers only.

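### The <1% early-release criterion cannot tell finished excretion from faecal excretion that has not yet arrived (minor)

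*Protocol*

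**What the plan says.** Protocol 8.1 plans residence up to 168 h (Day 8). Subjects may go earlier, as a group, on more than 90% cumulative recovery "or if <1% of the dose administered has been collected in urine and faeces within 2 separate consecutive 24 h periods". Once the criteria are met, "collection of all samples (blood, urine and faeces) will be stopped and the subjects will undergo discharge assessments". The same rule stands in the Synopsis (Section 3), Figure 1 footnote a, 10.3.3 ("collected in urine and faeces within 2 separate, consecutive 24 h periods") and Appendix 2 footnote a.

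If the criteria are not met by Day 8, residence may be extended by up to 48 h. After that, or if further residence is not thought appropriate or necessary, "then home collections of urine and/or faeces may be requested at the discretion of the investigator for individual subjects".

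Two other provisions bear on stool. Inclusion criterion 5 (9.2) selects men who average one to three stools a day, and 11.1 calls for action after 36 h without a bowel movement. Neither is linked to the release rule. No section makes the <1% criterion depend on a stool having been passed or on label having appeared in stool.

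**The concern.** A low amount collected over 48 h has two possible explanations: excretion is over, or the unabsorbed part of the dose has not yet come out. The <1% criterion treats them alike. The provisions on bowel habit concern passing stool, not label in stool. A man with slow transit can pass unlabelled stools, satisfy both provisions and still meet the criterion once his urine is low.

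Recovery in urine and faeces is a primary endpoint (Section 7), and stool that is not collected cannot be recovered later. The faecal share may be large: 5.3.1 gives oral bioavailability of about 50%, and 5.3.4 reports incomplete absorption in rats. An affected subject would show low total recovery and a distorted split between urine and faeces. The interval listings would reveal an empty or unlabelled last faecal interval, but not how much was missed. Because 5.3.4 also raises possible retention of label in cells, the shortfall could be mistaken for retention.

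**Working it through.** The protocol states no figure for this rule, so there is nothing to reproduce. The check asks when urine alone permits the criterion, and how often a subject is then released short.

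**Step 1: urine per 24 h period.** Let U be the urinary share of dose and h the half-life in hours. Period i (i = 0, 1, 2, ...) yields U × (2^(−24i/h) − 2^(−24(i+1)/h)). With U = 50% (taking bioavailability as fraction absorbed):

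| h | % of dose per successive 24 h | Earliest end of two periods <1% |
|---|---|---|
| 4 h | 49.2, 0.77, 0.01 | 72 h |
| 8 h | 43.8, 5.5, 0.68, 0.09 | 96 h |
| 12 h | 37.5, 9.4, 2.3, 0.59, 0.15 | 120 h |
| 22 h (pig terminal value, 5.3.4) | 26.5, 12.5, 5.8, 2.7, 1.3, 0.6, 0.3 | 168 h |

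Fast urinary clearance therefore opens the criterion from 72 h. At 22 h it permits no early release.

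**Step 2: simulation.** All inputs are assumptions:
- 6 subjects, with each one required to meet one of the two criteria before the group goes; cap at 168 h.
- Stool gaps gamma, shape 1 (irregular) or 4 (regular), at 1 or 2 stools per day.
- The 36 h provision always works, with a stool 0 to 12 h after the gap reaches 36 h.
- Arrival of label in stool lognormal, log-SD 0.35 between and 0.30 within subjects.
- Urine collection complete.

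The outcome is at least one subject who qualifies by the <1% criterion and is more than 10% of dose short at group release. With h = 4 h, a 50% faecal share and 40,000 trials per setting:

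| Median transit, stools | Current rule | + stool in later period | + label already in faeces |
|---|---|---|---|
| 24 h, all patterns | 0.01–0.07% | – | – |
| 36 h, 1/day irregular | 1.54% | 0.41% | 0.00% |
| 48 h, 1/day irregular | 8.82% | 3.74% | 0.00% |
| 48 h, 1/day regular | 7.73% | 4.56% | 0.00% |
| 48 h, 2/day irregular | 5.56% | 3.42% | 0.00% |
| 48 h, 2/day regular | 3.43% | 3.25% | 0.00% |

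The Monte Carlo standard error at 8.8% is √(0.088 × 0.912 / 40,000) = 0.14 points. Separately coded runs of the 48 h, 1/day irregular case gave 8.5% to 10.5%, hence about 9 to 10%.

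**Step 3: how it happens.** In that case the qualifying pair was a stool then none in 58% of affected subjects, none then a stool in 12%, and stools in both periods with <1% in 30%. Two stool-free periods did not occur.

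**Step 4: sensitivity at 48 h transit.**
- h = 6 h: at most 1.1%; 8 h: 0.5%; 12 h: 0.03%; 22 h: 0 in 20,000 trials.
- h = 4 h with a 30% faecal share: at most 1.9%.
- h = 4 h with a tenth of the urinary part leaving at 22 h: at most 0.54%.
- h = 4 h with 15% of dose never excreted (45% urine, 40% faeces): 1.6 to 2.2%.

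**Step 5: effect on the result.** With a 50% faecal share an affected subject is about 30 to 50% of dose short. One such subject moves the mean by at most 50/6 = 8.3 points, or 50/4 = 12.5 points with the minimum of 4 evaluable.

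**The case against.** The strongest reply is that the event needs an unlikely combination. Subjects are selected for at least one stool a day, 11.1 acts at 36 h, and all six must qualify before anyone leaves. The 4 h half-life and 48 h transit are not in the protocol. Much of the disposition data in 5.3.4 is multi-phase (rapid then slow elimination in rats, tri-exponential in pigs), which keeps urine above 1% per day for longer. This stands as to size. It does not settle the matter, because the rat data in 5.3.1 (very low concentrations after 24 h) point the other way, and none of the safeguards is part of the rule.

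Four stronger readings are tempting, and the documents do not support them.

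- *The rule contradicts 5.3.2.1*, which plans discharge after the dose has been eliminated. That passage states a plan and concerns biotin interference with laboratory tests. Unabsorbed label in the gut does not bear on that risk.
- *The evaluability test in 8.4 has the same fault*, since it also uses "or have <1% of the administered dose eliminated in excreta for 2 consecutive days, whichever is sooner". First-day urine is 26 to 49% of dose in Step 1, so the earliest qualifying pair ends at 72 h. By then "mass balance and PK samples for up to 72 h (up to Day 4) after IMP administration" already make the subject evaluable.
- *Two days without any stool would release a subject.* If the 36 h provision works as modelled, this does not occur.
- *Most trials would be affected if transit is slow.* In a similar model, the chance that at least one of 6 has his first labelled stool after 72 h is 59 to 90% at 48 h median arrival. That ignores group release: collection goes on until the last subject qualifies.

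**Conclusion.** The gap in the text is real: the <1% criterion can be met before faecal label has arrived, and meeting it ends collection. The extension and home-collection provisions mainly serve subjects who have not met the criteria, so they do not reliably catch this case. The consequence is an uncommon, single-subject understatement of recovery, not a general bias, and the grade is minor.

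The risk is negligible at 24 h median transit and about 1.5% of trials at 36 h. It reaches 9 to 10% only where fast urinary clearance, 48 h transit, a faecal share near 50% and one irregular stool per day coincide. Confidence is medium, because the protocol supplies none of the human values that decide where this trial lies.

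**What to change.** In 8.1, with cross-references in Section 3, Figure 1 footnote a, 10.3.3 and Appendix 2 footnote a, add:

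> For release before Day 8, the <1% criterion counts only if urine collection was complete in both 24 h periods and at least one faecal sample was collected in the later period.

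This is the core change. At 48 h transit it cuts the modelled risk by more than half with one irregular stool a day (8.82% to 3.74%), but does little with two regular stools a day (3.43% to 3.25%). The urine clause guards against a missed void and plays no part in these figures.

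Optionally, and again only for release before Day 8, require that at least 1% of dose has been recovered in faeces in an earlier period. This removes the rest of the modelled risk.

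The >90% criterion stays as written. From Day 8 so do the <1% criterion, the extension and the home-collection provisions, so the change cannot by itself trigger them. That limit is essential. Applied beyond Day 8, with 80% of dose in urine and 2% in faeces, the label condition would leave 17 to 75% of simulated trials with a subject still short of the criteria at 168 h (100% at 85% and 1%), although excretion was complete. Section 8.4 needs no change.

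The cost is some delay to early release within the planned 168 h. The stool condition adds about 0 to 2.5 h to mean group release in the main settings, and roughly 10 to 17 h when faecal excretion is very low. The label condition can remove early release altogether when faecal excretion is about 1 to 2% of dose and 90% recovery is not reached. No new data are needed beyond the collection records and interval results that the rule already uses.
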